## What's the main question being asked or hypothesis being tested in this study?

To determine whether participants randomized to an online single session intervention (SSI) targeting non-suicidal self-injurious behavior ("Project SAVE") endorse:

1. Lower self-reported *likelihood* of future non-suicidal self injury immediately post-intervention (secondary outcome)
2. Lower self-reported *frequency* of suicidal ideation (in the past 3 months) at 3 month follow-up (secondary outcome)
3. Lower self-reported *frequency* of non-suicidal self-injury (in the past 3 months) at 3 month follow-up (primary outcome)

relative to those randomized to an active control condition (i.e. supportive therapy SSI; Schleider & Weisz, 2018) in a large sample of cisgender heterosexual & sexual and gender minority teenagers ages 13-16 years old.

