## Describe the key dependent variable(s) specifying how they will be measured.

Our primary and secondary dependent variables will be measured using the self-report version of the Self-Injurious Thoughts and Behaviors Interview-R (SITBI-R; Fox, Harris, Wang, Millner, Deming, & Nock, 2020). Items in this measure ask participants about their attitudes/beliefs/history concerning various self-injurious thoughts and behaviors, including suicidal ideation (SI) and non-suicidal self-injury (NSSI). While our participants will complete all questions from the SITBI-R, the present study evaluates items that measure past 3-month frequency of NSSI, past 3-month frequency of SI, likelihood of future NSSI (see below section).

[https://shirleywang.rbind.io/papers/Fox\\_psychassess\\_2020.pdf](https://shirleywang.rbind.io/papers/Fox_psychassess_2020.pdf)

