***Testing Hypothesis 2: Do teenagers in the Project SAVE SSI condition endorse lower frequency of SI in the past 3 months—relative to teenagers in the active control program?***

First, we create our secondary outcome variable (i.e. frequency of SI in the past 3 months) by imputing values equal to 0 for participants who endorsed zero SI in the previous 3 months in an earlier question. See “SI Frequency in the Past 3 Months” under the key dependent variables section for more details.

Next, we will determine whether a Poisson regression, a negative binomial regression, a zero-inflated Poisson regression, or a zero-inflated negative binomial regression is most appropriate for analyzing our past 3-month frequency outcome (count variable). To do this, we will run all four models, conducting model fit tests to compare AIC values, BIC values, and raw scores for each regression. If all three indices agree (i.e. select the same “best” model of the four possible), we will interpret the results of that regression. If they do not agree (i.e. select different “best” models from the four possible), we will report the results from each of the selected models.

Regardless of model type, we will enter pre-intervention past 3-month frequency of SI as a covariate, and treatment condition as a predictor, of past 3-month frequency of SI at follow-up in the chosen regression(s). We will consider a *p* value of less than .05 for the treatment condition coefficient (in favor of the Project SAVE SSI) as a significant effect of the Project SAVE treatment on frequency of SI in the past 3-months.

***Testing Hypothesis 3: Do teenagers in the Project SAVE SSI condition endorse lower frequency of NSSI in the past 3 months—relative to teenagers in the active control program?***

We will follow the same procedures for hypothesis 2 but replacing “SI frequency in the past 3 months” with “NSSI frequency in the past 3 months.”

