### ***Imputing Data***

After excluding individuals based on the above criteria, we will impute any missing data in our variables of interest (pre- and post-intervention likelihood of future NSSI; pre- and post-intervention desire for future NSSI; past 3-month frequency of NSSI at pre-intervention and follow-up). To do this, we will execute an expectation-maximization and bootstrapping algorithm via the Amelia II package in R (Honaker, King, & Blackwell, 2011; <https://cran.r-project.org/web/packages/Amelia/Amelia.pdf>). All variables from the corresponding statistical model (i.e. hypothesis tests 1 - 3) will be included in the algorithm used to create the imputed data for that test: (a) baseline values for the outcome—likelihood of NSSI, desire for NSSI, or past 3-month frequency of NSSI, (b) follow-up values for the outcome, and (c) condition assignment, as well as (d) other baseline variables that are likely associated with each outcome variable (for **past 3-month frequency of NSSI at follow-up**: lifetime history of NSSI (y/n), past-month frequency of NSSI, past-year frequency of NSSI, and lifetime frequency of NSSI at baseline; for **likelihood of NSSI post-intervention**: all of these same variables plus past 3-month frequency of NSSI at baseline; for **past 3-month frequency of SI at follow-up**: lifetime history of SI (y/n), past-month frequency of SI, past 3-month frequency of SI, past-year frequency of SI, and lifetime frequency of SI at baseline). Together, these variables (a - d) will be used to create the imputed datasets for each of our three hypotheses.

The number of imputed datasets we create will equal the percentage of missing data for each of our three outcome variables (post-intervention likelihood of NSSI, post-intervention desire for future NSSI, past 3-month frequency at follow-up), rounded up to the next integer value. For example, we will create 7 imputed datasets to test hypothesis 1 if 6.2% of the data for the post-intervention likelihood of NSSI outcome variable is missing. We will create 8 imputed datasets to test hypothesis 2 if 7.6% of the data for the post-intervention desire for future NSSI outcome variable is missing.

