### ***Additional Exploratory Analyses***

Additional secondary analyses will:

- (1) employ predictive modeling techniques to predict which individuals benefited from, vs. did not benefit from, the Project SAVE intervention program.
- (2) evaluate cross-sectional relationships between other variables collected within the SITBI-R and Self-Hate Scale (e.g. desire to stop future NSSI; likelihood of future NSSI; self-hatred).

These analyses will not be conducted nor reported in the present paper, and a more detailed pre-registration will be submitted at a later date.

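### The imputation rule gives hypothesis 2 the wrong outcome (desire for future NSSI instead of SI frequency), and the winsorising list omits SI frequency

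*Combined protocol and SAP*

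**What the plan says.** **What hypothesis 2 is.** The main-question section makes SI frequency at 3-month follow-up a secondary outcome. The section on key dependent variables says "the present study evaluates items that measure past 3-month frequency of NSSI, past 3-month frequency of SI, likelihood of future NSSI". Under Testing Hypothesis 2, the regression will "enter pre-intervention past 3-month frequency of SI as a covariate, and treatment condition as a predictor, of past 3-month frequency of SI" at follow-up.

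**What Imputing Data says.** Desire for NSSI appears four times:

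- in the list of variables to impute: "pre- and post-intervention desire for future NSSI; past 3-month frequency of NSSI at pre-intervention and follow-up";
- in item (a) of the imputation model: "desire for NSSI, or past 3-month frequency of NSSI, (b) follow-up values for the outcome";
- in the list of three outcomes whose missingness sets the number of datasets: "post-intervention likelihood of NSSI, post-intervention desire for future NSSI, past 3-month frequency at follow-up";
- in the worked example, where the team will "create 8 imputed datasets to test hypothesis 2 if 7.6% of the data for the post-intervention desire for future NSSI outcome variable" is missing.

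The same section also says that each imputation model contains all variables of the matching hypothesis test. Its item (d) names SI frequency at follow-up, with SI history and SI frequency at baseline as predictors.

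**What Winsorizing Outliers says.** Two count variables will be capped at their 95th percentile before hypotheses 2 and 3 are tested. The bracketed list gives NSSI frequency at baseline and at follow-up. The SI Frequency paragraph under Secondary Dependent Variables sends the reader to that subsection for its outlier rule.

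**The concern.** Two operative rules do not match the hypothesis they serve. Read literally, the number of imputed datasets for hypothesis 2 is set by a variable that hypothesis 2 does not use. That variable also belongs to the wrong assessment: it is labelled post-intervention, so it comes from the first session, whereas SI frequency is collected three months later. The plan itself tests dropout separately at these two points.

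For winsorising, SI days are typed into an open text box, and the plan states no upper limit. Whether extreme entries are capped affects both the outcome and the baseline covariate of a confirmatory count model. The list supports leaving SI raw; the cross-reference and the mention of hypothesis 2 support capping it. An analyst could cite either after seeing the data, and a pre-registration is meant to prevent that. Hypothesis 2 also shares the false discovery rate correction with the primary test, so its p value can alter the adjusted primary p value.

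**Working it through.** **1. The plan's own figures.** The rule is: number of datasets = percentage missing, rounded up. 6.2 gives 7 (hypothesis 1 example) and 7.6 gives 8 (hypothesis 2 example). Both reproduce. The error is in the variable named, not in the arithmetic.

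**2. Cross-check of names.**

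| Place | Variable for hypothesis 2 |
|---|---|
| Main question; key dependent variables; Testing Hypothesis 2 | SI frequency |
| Imputing Data: variables to impute | desire for NSSI |
| Imputing Data: item (a) | desire for NSSI |
| Imputing Data: item (d) | SI frequency |
| Imputing Data: outcomes that set the number of datasets | desire for NSSI |
| Imputing Data: worked example | desire for NSSI |
| Winsorizing Outliers | none (NSSI frequency only) |

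The only other mention of desire is under Additional Exploratory Analyses ("desire to stop future NSSI; likelihood of future NSSI; self-hatred"). It is a differently worded item, in analyses this paper will not report. The third entry in the list that sets the number of datasets does not say whether it means NSSI or SI.

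**3. Effect on the number of datasets.** The documents give no expected SI missingness, so 10–40% is assumed. The fraction of missing information (FMI) is set equal to the missing fraction, also an assumption. Relative efficiency is 1/(1 + FMI/M). The standard-error ratio is √[(1 + FMI/8)/(1 + FMI/M)], with M in the denominator equal to the percentage missing.

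| SI missing | M by the rule | Efficiency, M = 8 | Efficiency, M by the rule | SE ratio |
|---|---|---|---|---|
| 10% | 10 | 1/1.0125 = 0.988 | 1/1.01 = 0.990 | 1.001 |
| 20% | 20 | 1/1.025 = 0.976 | 0.990 | 1.007 |
| 30% | 30 | 1/1.0375 = 0.964 | 0.990 | 1.014 |
| 40% | 40 | 1/1.05 = 0.952 | 0.990 | 1.020 |

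M = 8 is the plan's example, used here for the case in which few first-session answers are missing but many follow-up SI answers are.

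**4. Reach of the winsorising gap.** Hypotheses 2 and 3 use 2 outcomes × 2 time points = 4 count variables; 2 are named. Values above the 95th percentile: 0.05 × 500 = 25 at most per time point. Among observed follow-up values only, this is 0.05 × 450 = 22.5 at 10% missing and 0.05 × 300 = 15 at 40% missing.

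**5. Can the choice change a conclusion?** This was an illustrative simulation with every input assumed except the arm size:

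- 300 trials per scenario, 250 per arm, complete data;
- negative binomial regression of follow-up SI on baseline SI and condition;
- latent correlation 0.5, true rate ratio 0.75, uncorrected p;
- counts limited to 92, the most days in any 3 calendar months;
- SI left raw, against both SI variables capped at their 95th percentile.

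| Scenario | Disagree on p < .05, entries ≤ 92 | Disagree, 1% of entries at 93–365 |
|---|---|---|
| mean 15, k = 0.5 | 7.3% | 26.2% (279 of 300 trials converged in both fits) |
| mean 25, k = 0.7 | 2.0% | 19.0% |

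Two repeat runs with other seeds gave 3.7–7.3% with valid entries and 20.7–24% with contamination. With no true effect, the repeats gave 0.3–2.3% and 5.3–11%.

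**The case against.** The strongest reply is that nobody would be misled. The SI imputation model can be recovered: the section calls for all variables of the matching test, and item (d) names SI frequency with its own predictors. For winsorising, the SI paragraph points to that subsection by name, and the subsection mentions hypothesis 2. Its reference to two count variables could even mean NSSI and SI, with the bracket left unrevised. On this view it is an incomplete text replacement, not two competing plans.

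Much of that stands. Intent is clear, and the effect on the number of datasets is negligible to small. The plan also repeats all three tests on non-imputed data and will discuss any differences, so an effect of the imputation slip would be visible. That repeat does nothing for winsorising.

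The simulation also deserves discounting. The higher disagreement rates need 1% of answers to be impossible for a 3-month day count, and nothing in the documents supports that rate. The runs use uncorrected p values, one of the four candidate models and complete data. The effect was set where power is moderate, which raises disagreement. The 2–7% range with valid entries is the safer guide.

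What does not stand is the step from clear intent to no change needed. The listed rules still contradict the hypotheses, and the winsorising list can be cited to support leaving SI raw.

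**Conclusion.** The concern holds: the text is wrong as written and should be corrected, with high confidence. On the number of datasets the consequence is small, a standard error at most 2.0% larger under the assumptions shown. On winsorising it is larger but uncertain: up to about 25 SI values per time point are affected, with a changed significance call in roughly 2–7% of simulated trials with valid entries and 19–26% with 1% impossible entries. These are illustrations, not forecasts.

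The damage is confined to a secondary but confirmatory outcome. The variables of the primary outcome, NSSI frequency, are correctly listed for imputation and winsorising. The primary is exposed only through the shared false discovery rate correction, and that indirect effect was not quantified.

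**What to change.** In Imputing Data, replace desire for (future) NSSI with past 3-month SI frequency in all four places, at baseline, at follow-up or both as each place requires. In the hypothesis 2 example and in the list of outcomes that sets the number of datasets, the time point becomes the 3-month follow-up. In that list, also label the third entry as NSSI frequency. The example's arithmetic stays the same: 7.6% missing still gives 8.

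In Winsorizing Outliers, list four count variables: NSSI frequency and SI frequency, each at baseline and at 3-month follow-up.

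The cost is four replacements, one label and one list. No analysis is added and the sample size does not change. The plan states that no data have been collected, so the edits can be made without knowledge of results.

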### ***Winsorizing Outliers***

We will winsorize outliers in our two count variables of interest (past 3-month frequency of NSSI at pre-intervention and follow-up) before running tests for hypothesis 2 and 3. Outliers will be defined as values above the 95th percentile for the variable in question, calculated using the Winsorize() function in the DescTools package in R (Singnorell et al., 2020, <https://cran.r-project.org/web/packages/DescTools/DescTools.pdf>).

[project.org/web/packages/DescTools/DescTools.pdf](https://project.org/web/packages/DescTools/DescTools.pdf)); flagged outliers will be replaced with the 95th percentile value.

**How many observations will be collected or what will determine the sample size? No need to justify decision, but be precise about exactly how the number will be determined. (optional)**

The final sample size for *collected* data will be  $N = 500$  randomized participants (250 per condition) who meet our type 1 inclusion criteria (i.e. who are not excluded by type 1 exclusion criteria outlined in the above section). The total number of participants who provide *usable* data will then be determined by the number of participants who meet our type 2 inclusion criteria (i.e. who are not excluded by type 2 exclusion criteria outlined above). Therefore, the present study will have a maximum of 500 participants, with a final sample size determined by the number of participants meeting our type 2 inclusion criteria specified above.

**Other. Anything else you would like to pre-register? (e.g., secondary analyses, variables collected for exploratory purposes, unusual analyses planned?) (optional)**

### ***Anticipated Sample Demographics***

The present study will recruit research participants via online social media advertisements. Based on samples recruited for other studies by members of this research team (using similar recruitment procedures; Fox et al., 2020, <https://doi.org/10.1037/ccp0000486>; Smith, Fox, Carter, Thoma, & Hooley, *in press*), we anticipate the following demographic representation among the present study's research participants:

65-75% White  
5-15% Asian  
5-15% Latinx  
5-15% Black

The present investigators will recruit participants with the explicit goal of increasing racial diversity and representation among our research participants (see Roberts et al., 2020; <https://doi.org/10.1177%2F1745691620927709>). If we fail to meet the anticipated percentages for Asian, Latinx, or Black participants outlined above, we will specifically address lack of racial diversity as a potential limitation of generalizability within the text of the treatment results paper.

Additionally, we plan to recruit approximately 50% sexual or gender minority (SGM)-identifying participants via online advertisements that target LGBTQ+ interests/groups as well as advertisements targeted toward the general teen population.

### ***Treatment Effects Among SSI Completers***

An exploratory analysis will examine whether or not treatment assignment is a significant predictor of our primary outcome (i.e. NSSI frequency in the past 3 months at follow-up in SAVE vs. control conditions), *among participants who have completed an SSI*. To do this, we will run the same procedures as above for testing hypothesis 3—among the subsample of participants who completed a full online program (either Project SAVE SSI or the active control group SSI).

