**Specify exactly which analyses you will conduct to examine the main question/hypothesis. (optional)**

***Testing for Differential Dropout***

First, we will test for differential dropout by study condition. To do this, we will use Z-tests of differential proportions where we compare the proportion of people who drop out before completing the study (Y or N) as a function of treatment condition (0 = control group SSI, 1 = Project SAVE SSI). We will run two tests evaluating differential dropout: (1) measuring dropout prior to finishing our post-intervention questions, and (2) measuring dropout prior to finishing our 3-month follow-up questions. To be considered a study “completer” for the post-intervention questions, a participant must have made it through all post-intervention survey sections (i.e. all sections but “final block” section that presents information for study logistics). To be considered a study “completer” for the 3-month follow-up questions, a participant must have made it through all follow-up survey sections (i.e. all sections but “final block” section that presents information for study logistics).

If the *p* value is greater than .05 we will assume dropout was not dependent on condition assignment and can proceed with interpreting the effects of intervention assignment (i.e. proceed with the between-group analyses exactly as described below, starting in the section labeled “Hypothesis 1”).

If the *p* value for this test is less than .05 we will conclude that dropout was dependent on condition assignment, and we will take the following steps to improve the interpretability of our results. Unequal dropout between treatment groups can introduce bias in trial results; however, this is not always the case (Bell, Kenward, Fairclough, & Horton, 2013; <https://doi.org/10.1136/bmj.e8668>). One major concern is that, if data are *not missing at random*, systematic differences may exist between “dropouts” and “completers” that cannot be corrected for, limiting the interpretability of our results. For example, if more control condition participants experienced a worsening of clinical symptoms and dropped out before completing follow-up measures, this worsening of symptoms would not be captured by completers’ data (or by data imputed based on the available completers’ data). Thus, should unequal dropout exist

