### ***Correcting for Multiple Comparisons***

We will use a false discovery rate approach to correct for multiple comparisons among our main confirmatory tests of hypotheses 1 - 3. As such, in all places where a significant effect is defined by a *p* value less than .05, this is referring to the post-correction *p* value (i.e. the *p* value after correction using the false discovery rate method).

***Outliers and Exclusions. Describe exactly how outliers will be defined and handled, and your precise rule(s) for excluding observations. (optional)***

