### ***Type 1 Exclusions***

Type 1 exclusions are exclusions that can be automated and do not require consensus among investigators. A research team member who will not be involved with conducting the primary study analyses will use type 1 exclusions to determine when participant recruitment is complete. Recruitment for the present study will end once 500 participants have been randomized *who pass all type 1 exclusions tests* (i.e. are still eligible for inclusion after excluding for type 1 criteria; see our section on sample size for more details).

Here, we will exclude participants that fail to meet the following study inclusion criteria:

- Must be 13 - 16 years old at the time of the baseline survey
- Must report comfort reading and writing in English

- Must endorse no learning disability, visual impairment, or other difficulty that makes it difficult to answer questions on a computer
- Must have access to a laptop or smartphone with internet access
- Must endorse purposefully hurting self without wanting to die within the past month
- Must endorse *either* “I do not like myself” or “I hate myself” on CDI-II item 7 in a screener survey

Here, we will exclude the following participants based on failure to meet the following quality check criteria:

- Participants who exit the study *prior* to condition randomization for our listed analyses (note: the present study will use an intention-to-treat approach, where every participant who was randomized to a study condition—and who is not excluded for one of the specific reasons outlined in this section—will be included in our analyses)

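### The exploratory completer analysis compares groups formed after randomisation by two different programs, so it can show a spurious SAVE benefit or hide a real one even when completion proportions are equal

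*Combined protocol and SAP*

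**What the plan says.** The section Treatment Effects Among SSI Completers, under the Other heading, states: "An exploratory analysis will examine whether or not treatment assignment is a significant predictor of our primary outcome". The method is brief: "we will run the same procedures as above for testing hypothesis 3", applied "among the subsample of participants who completed a full online program (either Project SAVE SSI or the active control group SSI".

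Hypothesis 3 takes its model from hypothesis 2 with NSSI in place of suicidal ideation (SI). Under Testing Hypothesis 2, the pre-intervention frequency of the outcome enters "as a covariate, and treatment condition as a predictor, of past 3-month frequency of SI at follow-up in the chosen regression(s". No other covariate is named.

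Elsewhere, Type 1 Exclusions says "the present study will use an intention-to-treat approach", subject to listed exclusions. The false discovery rate method is used to "correct for multiple comparisons among our main confirmatory tests of hypotheses 1 - 3", so the completer analysis lies outside it. Testing for Differential Dropout warns that, where missingness is informative, "systematic differences may exist between “dropouts” and “completers” that cannot be corrected for, limiting the interpretability of our results". The completer section repeats no such caution. It also does not say what counts as completing a program; the plan defines a completer only for the post-intervention and follow-up surveys.

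**The concern.** Randomisation makes the two arms comparable, but not the subsets that go on to finish. SAVE addresses self-injury directly with cognitive and dialectical behaviour therapy components, while the control encourages sharing feelings. The youths who abandon one need not resemble those who abandon the other. If those with more persistent self-injury leave SAVE more readily, the remaining SAVE group looks better with no treatment effect. If they leave the control more readily, a real effect can be masked. The baseline NSSI count captures only part of what drives both leaving and later self-injury.

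What is at stake is the reading of a result on the primary outcome. The two exploratory sections that follow (SGM-identifying youth, and additional analyses) say that their results stay out of the present paper. The completer section does not, so its result may be printed beside the intention-to-treat result and taken as the effect of finishing the session.

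**Working it through.** **1. What the plan fixes.** There are 500 randomised participants at 1:1, so 500/2 = 250 per arm. It gives no completion rates, dropout rates, effect size or variability, so there is no figure for this analysis to reproduce. Everything below rests on assumed inputs.

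**2. Mechanism.** Assume no true effect and set each arm's mean count to 1. If a share q of an arm does not complete and would have mean k, the completers' mean is (1 - qk)/(1 - q).

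- q = 0.20 in both arms, k = 1.5 in SAVE and 1 in control: (1 - 0.30)/0.80 = 0.875 against 1. The ratio is 0.875 although both arms have 80% completion.
- q = 0.20 and k = 1.5 in both arms: ratio 1.00.
- q = 0.20 in SAVE and 0.10 in control, k = 1.5 in both: 0.875/[(1 - 0.15)/0.90] = 0.875/0.944 = 0.93.

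Here k is the excess left after baseline adjustment, so these figures show how the bias arises, not its likely size.

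**3. Simulation that includes the baseline adjustment.** There were 1,000 runs per scenario with 250 per arm and a true rate ratio of 1. Counts were negative binomial (size parameter 1.5), capped at the 95th percentile. The severity driving follow-up counts had correlation 0.6 with the trait driving baseline counts. The analysis was a negative binomial regression on treatment and log(1 + baseline count), two-sided 5% level (the plan does not state sidedness). Selective exit means that the log-odds of completing fall by 1 per standard deviation of severity, unless noted.

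| Completion, SAVE / control | Selective exit | Completers' rate ratio | Significant for SAVE | Significant for control | Completion Z-test significant |
|---|---|---|---|---|---|
| 80% / 80% | alike in both | 1.00 | 3.5% | 3.3% | 4.1% |
| 80% / 80% | SAVE only | 0.92 | 12.8% | 0.1% | 5.6% |
| 70% / 80% | SAVE only | 0.88 | 21.6% | 0.0% | 72.5% |
| 70% / 80% | alike in both | 0.96 | 6.5% | 0.8% | 77.6% |
| 70% / 85% | SAVE; half the slope in control | 0.91 | 15.8% | 0.4% | 98.8% |
| 80% / 80% | opposite directions (extreme) | 0.85 | 37.3% | 0.0% | 5.9% |
| 80% / 80% | control only | 1.10 | 0.1% | 12.9% | 4.2% |

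The nominal rate in each direction is 2.5%. Analysing everyone randomised, with outcomes assumed observed for all, gave rate ratios of 0.995-1.002, significant in 3-6% of runs and in favour of SAVE in 2-3%.

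**4. What a test of proportions can show.** Power at 250 per arm is approximately Φ[(|p1 - p2| - 1.96·s0)/s1], where s0 and s1 are the pooled and unpooled standard errors. For 80% v 75%: s0 = √(2 × 0.775 × 0.225/250) = 0.0373 and s1 = √((0.16 + 0.1875)/250) = 0.0373, giving 27%. The same formula gives 39% for 90% v 85% and 73% for 80% v 70%. A non-significant result is weak evidence of equal completion. In the second row of the table the proportions really are equal, so no such test can reveal the bias.

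**The case against.** The strongest reply is that little depends on this analysis. It is labelled exploratory, sits outside the multiplicity correction, and leaves hypothesis 3 intention-to-treat. That stands. A reader might infer that the primary conclusion is compromised; the documents do not support this, because no confirmatory test uses the completer subset.

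The bias also vanishes if selection works alike in both arms at similar completion rates. That stands too, but nothing in the plan makes it likely or checks it.

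A reader might infer from the formula in step 2 that, at 20% non-completion, selection alone would mimic a 12-25% reduction (k = 1.5 to 2). That is too strong. It assumes one-sided selection left over after baseline adjustment. With k = 2, completers average (1 - 0.40)/0.80 = 0.75, so non-completers would self-injure at 2/0.75 = 2.67 times their rate. Nothing in the documents supports that. Eligibility requires past-month self-injury and counts are capped at the 95th percentile, both of which narrow such contrasts.

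A reader might also infer that the dropout Z-tests miss youths who quit the program. The first test counts dropout before the end of the post-intervention questions, so those youths would ordinarily be included. Its limit is that it compares proportions, not the kind of participant who leaves. The percentile-based sensitivity analysis follows only a significant Z-test and addresses missing outcomes, not selection into a completer subset.

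**Conclusion.** The point holds as a limitation of one exploratory result. The completer comparison is not protected by randomisation, and adjustment for baseline NSSI count alone does not restore comparability. The direction of bias cannot be known in advance.

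Under the assumptions in step 3, one-sided selective exit moves the rate ratio to about 0.88-0.92, or about 1.10 in the mirror case. At 80% completion in both arms, the rate of significant findings in the favoured direction rises from a nominal 2.5% to about 13%. Like selection at equal completion gives 1.00. These figures depend on assumed completion rates and an assumed link between severity and leaving, and the simulation fitted only one of the plan's four candidate count models. They show what is possible, not what to expect in this trial.

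**What to change.** In Treatment Effects Among SSI Completers:

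- Define what counts as completing each program, separately from completing the surveys.
- Weight each arm's completers by the inverse probability of completion, estimated within arm from baseline variables already collected: NSSI and SI frequency, likelihood of NSSI, self-hate, age and SGM status. Each arm's completers then resemble their whole arm on those variables.
- Report completion proportions and completers' baseline characteristics by arm.
- Present the result as a non-randomised, descriptive comparison that is not evidence of efficacy.

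A complier average causal effect of finishing SAVE, with assignment as the instrument, may be added as an optional sensitivity analysis. It should not be a required replacement, because it answers a different question and assumes that unfinished SAVE has no effect relative to control. SAVE has four content sections, so a youth who leaves late has received most of it. If partial exposure helps, the estimate exaggerates the benefit, and the plan should say so.

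The cost is a paragraph of text and a little analysis work, with no new data or participants. Weighting slightly lowers precision and removes only the selection that the measured variables capture; unmeasured selection remains.
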